Protocol Template Guidance

For Submissions to CORIHS

TITLE: Aromatherapy for management of back pain in the Emergency Department

INVESTIGATORS: [name] MD / [name] MD / [name] BS
Department of Emergency Medicine

A. SPECIFIC AIMS

This study aims to research the use of aromatherapy for pain control in the emergency department, specifically, acute back pain. Aromatherapy, particularly Rose Essential Oil (Rosa damascena) has been studied in recent literature and shown to be effective versus placebos for the control of acute pain with lasting effects during burn dressing changes and post-operative pain management. These studies have been small and specific to discrete clinical conditions. Their evidence supports the use of aromatherapy for acute pain control with additional patient satisfaction benefit, but they are not yet externally validated to more common conditions facing emergency medicine physicians. We chose to study acute isolated back pain and sciatica presenting to the emergency department and the use of Rosa damascena essential oil versus a control of Almond Oil for the treatment of isolated back pain and sciatica. We will investigate the use of aromatherapy in pain management by measuring and comparing pre- and post-treatment pain levels using a 100 mm visual analog scale (VAS) for pain. A significant reduction in pain by 13 mm on the VAS has been previously demonstrated as the minimal clinically important difference for treatment of pain (). Our primary endpoint will be the evaluation of significant change in VAS score greater than 13 mm between both groups immediately following a 30 minute blinded aromatherapy treatment and again 30 minutes later. Our secondary measures include patient satisfaction, need to rescue medication (its type and dose), and subjective changes in pain.

B. Background and Significance

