Aromatherapy has been hypothesized to be an effective management strategy for acute pain control. Its use has been recently demonstrated in Iran, using Rosa damascene (Damask Rose) essential oil. Rosa damascene is believed to possess anti-anxiolytic, sedative, anticonvulsive, and analgesic effect on the CNS when delivered through the olfactory system (Mohebitabar et al. 2016). This theory is believed to be in part due to the lateral gate theory of pain control and a stimulant's ability to inhibit transmission of stimuli through pain fibers. However, while any olfactory stimulant might be hypothesized to do just that, only Rosa damascena has been shown to produce significant reduction in pain on the VAS as well as patient satisfaction when compared to scented placebos like Almond Oil. Rosa damascene has been shown to improve pain control during dressing changes of second- and third-degree burns (Bikmoradi et al 2016). It has also been shown effective and equal to NSAID treatment of immediate post-operative pain in children (Marofi et al. 2015). It may be an affordable and easy-to-use modality for pain control in the emergency department. Its prior studies are small in sample size and carry little external validity that could be applied to an American Emergency Department population. We aim to assess whether aromatherapy using Rosa Damascena is reproducible in the emergency department for control of isolated and acute back pain, two common painful conditions seen with poor evidence for proper pain control. Validity of Rosa damascene aromatherapy in acute back pain and sciatica may open new doors of pain control to be researched in the emergency department and will further characterize the use of aromatherapy in modern medicine.

C. Preliminary Studies

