Patients will be recruited into this study by an investigator in the Stony Brook Emergency Department. A sample size was calculated to be 30 patients for each treatment arm based on a power of 0.80, desired p value below 0.05, and 95% confidence intervals with the anticipated possibility of patient loss or desire to withdraw during treatment. Patients will be approached for recruitment after an attending or resident physician has seen them and does not anticipate immediate need for narcotic pain medication, immediate imaging, or immediate threats to life or limb. Patients will be included by the attached inclusion and exclusion criteria. Double-blinding will be ensured by block randomization of each treatment arm, performed outside of the emergency department. In the Emergency Department Research Offices, the two treatment arms will be allocated into identical, individual vessels with only a codified label applied to each. Using block randomization, 30 treatments will be distributed to each arm in secret by a clinical research assistant or [name]. Each treatment will be codified individually and recorded in secrecy and kept from the investigators, [name] and [name]. Randomization will then arrange the total 60 treatments in longitudinal order for sequential random treatments to be selected as each patient is recruited.

Screening

Patients will be approached in private and the name, title, and role of the investigator explained after asking permission to speak with the patient. The patient will be told that we are conducting a clinical research trial for the treatment of acute back pain and sciatica. Aromatherapy will be explained as the treatment of interest and a modality that has been tested and proven in other types of pain. The use of Almond products and Rose products will be briefly discussed with the patients. Patient's will be asked about any allergies and then asked specifically about allergies to Almonds, Roses, perfume, and ibuprofen. Patient will be informed that speaking with the investigator is entirely optional, as is participating in the study, as there may be no direct benefit to them despite disclosure of their private information to the investigator. An Inclusion and Exclusion form will be reviewed with the patient and

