their chart, noting their sequential patient number in this study as the only de-identified patient ID. No PMI will be collected; no MRN, address, phone number, emails, name, SSN, DOB, chief complaint, PMH, PSH, or medications will be recorded. The risks and benefits will be explained to the patient including risk of allergy, risk of no change in pain, benefit of pain improvement, and benefit of contribution to medical research. The consent form will be reviewed in full and any questions answered. Those patients interested in participating and able to grant consent will do so.

Procedures

Rosa damascena 40% and Almond Oil 40% kept outside of the ED will be prepared each day and dispersed into identical vessels with randomized identification numbers. The coded numbers and their respective modality will be recorded by an investigator not involved in delivery and kept secured. Patients will be chosen into random treatment arms by block randomization and their coded treatment recorded on the patient data sheet. Patients will be given 4 drops of either modality (40%) on a cotton ball kept between 20 and 30 cm from their face for 30 minutes.

With regards to study blinding, the treatments will be randomly assigned and the patients will not be told which treatment they are receiving. The patients will be aware that the study involves Rose and Almond scents and will likely be able to identify the scent used in their treatment. However, at the end of the study procedures, an independent observer will assess the patient's pain after the aromatherapy has been removed from the room, and will not be aware of which patients received which treatment.

E. Statistics

VAS differences immediately after treatment and 30-minutes following will be aggregated from their respective 100 mm VAS for pain and the change calculated for each patient. One-tailed paired t-Tests will be then conducted on the means after standard deviation is calculated and compared between treatment and control groups. A chi-squared test will then be applied between both groups for analysis of significant differences in patient satisfaction and subjective reports of pre- and post-treatment pain. The use of rescue medications by type and dosage will be measured as a percentage of each group and compared via t-Test between both groups.

F. Funding

Rosa damascene and Almond Oil are affordable and readily available over-the-counter. This trial requires no significant funding to be conducted.

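### The primary VAS test is one-tailed with no reason given, and at the plan's only stated level (p < 0.05) it does not match the 95% confidence intervals named in the sample-size basis

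*Combined protocol and SAP*

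**What the plan says.** Section E, Statistics, analyses the change in VAS at the two post-treatment times as follows: "One-tailed paired t-Tests will be then conducted on the means", with the two arms then compared. It states no significance level, plans no confidence interval and does not explain the choice of one tail.

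The only level and the only interval in the document are in Section D, Study Sample, where 30 patients per arm are said to be "based on a power of 0.80, desired p value below 0.05, and 95% confidence intervals". That sentence does not say whether the level or the interval is one- or two-sided. It names no effect size, no SD and no dropout rate.

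Section A, Specific Aims, gives the primary endpoint as "evaluation of significant change in VAS score greater than 13 mm between both groups", at the end of treatment and 30 minutes later. Nothing in the document sets a one-sided level of 0.025, a 90% interval or a one-sided confidence bound, any of which would bring the test and the interval into line.

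**The concern.** A test and the interval reported with it should lead to the same conclusion. A one-tailed test at 0.05 puts the whole 5% in one direction, whereas a two-sided 95% interval leaves 2.5% on each side. The first is therefore an easier hurdle for rose than the second. A borderline difference could be called significant while its 95% interval still includes no effect. The chance of a false claim for rose would be double what a reader of a 95% interval assumes.

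The choice of tails also enters the sample-size calculation. Because Study Sample does not state it, the stated power of 0.80 cannot be tied to a particular test. Sidedness has to be settled before data are seen, because a choice made afterwards is not credible.

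**Working it through.** **Inputs from the document.** 30 per arm, 1:1 allocation; p below 0.05; 95% intervals; power 0.80 (all Section D, Study Sample); one tail (Section E); 13 mm as the minimal clinically important difference (Section A).

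**Assumptions.** The 0.05 and the 95% carry over from the sample-size sentence to the analysis. The interval is two-sided. The test compares the arms as independent groups, so df = 30 + 30 − 2 = 58. The SD of VAS change is not given, so 15 to 30 mm is shown. The sample-size sentence does not name 13 mm, so its use as the design difference is also an assumption.

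**1. The plan's own figure.** With n per arm = 2 × SD² × (z_alpha + z_power)² / 13², solve for the SD that gives n = 30, with no dropout:
- One-sided 0.05: SD = 13 × √15 / (1.645 + 0.842) = 20.2 mm.
- Two-sided 0.05: SD = 13 × √15 / (1.960 + 0.842) = 18.0 mm.

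Allowing for 10% dropout (27 per arm analysed), the implied SDs are 19.2 and 17.0 mm. For 20% dropout (24 per arm) they are 18.1 and 16.1 mm. So 30 per arm cannot be reproduced uniquely, and the document does not show which sidedness lies behind it.

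**2. Critical values at 58 df.** The one-tailed 0.05 test rejects when t exceeds 1.672. The two-sided 95% interval excludes zero on the side favouring rose only when t exceeds 2.002. Any t in between is significant by the test and inconclusive by the interval. This gap does not depend on the SD.

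**3. The window in millimetres.** SE = SD × √(2/30). The limits are 1.672 × SE and 2.002 × SE.

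| Assumed SD (mm) | SE (mm) | One-tailed test rejects from (mm) | 95% interval excludes zero from (mm) |
|---|---|---|---|
| 15 | 3.87 | 6.5 | 7.8 |
| 20 | 5.16 | 8.6 | 10.3 |
| 25 | 6.45 | 10.8 | 12.9 |
| 30 | 7.75 | 12.9 | 15.5 |

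Example at SD 20 mm: t = 1.8 is a difference of 9.3 mm. One-sided p = 0.039, two-sided p = 0.077, and the 95% interval is −1.0 to 19.6 mm.

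**4. How often a result falls in the window** (noncentral t, noncentrality = true difference / SE).
- No true effect: 0.050 − 0.025 = 0.025, whatever the SD.
- True 13 mm, SD 20 mm: power is 0.800 one-tailed and 0.697 two-sided, so the window probability is about 0.10.
- True 13 mm, SD from 18 to 30 mm: about 0.08 to 0.13.

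**5. If an observed difference above 13 mm were also required.** For a significant result above 13 mm to have a 95% interval that includes zero, 2.002 × SD × √(2/30) must exceed 13, so SD must exceed 25.2 mm. At SDs of 15, 20 and 25 mm the upper limits in the table are all below 13 mm, and the conflict could not occur.

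**6. Effect of a two-sided test on the design.** At 80% power the sample size rises by the ratio (2.802 / 2.486)² = 1.27. If 30 per arm was one-sided, holding 0.80 would need 30 × 1.27 = 38.1, so about 38 to 39 per arm; keeping 30 gives about 0.70. If 30 per arm was already two-sided, power stays near 0.80.

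**The case against.** The best defence is that the hypothesis is directional: rose is the active treatment, almond is the control, and the trial asks whether an earlier benefit can be reproduced. A one-tailed test is a recognised choice for such a question. Also, Section E plans no confidence interval, and the 95% in Study Sample could mean a one-sided bound, which would agree exactly with a one-tailed 0.05 test. Finally, if the endpoint in Section A requires more than 13 mm observed between arms, the conflict disappears at SDs up to about 25 mm.

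Much of this stands as a limit on the point. The two-sided reading of the interval is conventional but inferred, and the 13 mm condition matters. The defence does not supply a justification for one tail, a level chosen for it or a matching interval. Section E contains no 13 mm rule. If the 0.05 does not carry over from Study Sample, the primary test has no stated level at all, which would also need correcting.

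A reader might infer more than the document supports:
- *That the aim is non-directional.* Only the endpoint sentence lacks a direction. The rest of Section A and Section B expect rose to do better.
- *That the plan itself expects rose might be worse.* The remark in Section B that "any olfactory stimulant might be hypothesized to do just that" is one clause of a sentence that goes on to single out rose as better than scented placebos. The clause alone would suggest no difference, not inferiority. The risks listed in Section G, such as uncontrolled pain or dislike of the scent, apply to both arms.
- *That the primary outcome is held to a weaker standard than every secondary outcome.* Rescue medication is compared by a t-test whose sidedness is not stated.
- *That the trial is underpowered.* That depends on an SD and a sidedness that the document does not give.

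**Conclusion.** The point holds in a limited form. The plan specifies a one-tailed primary test without a reason, and its only stated level and interval do not match on the conventional reading. For a between-arm test at 58 df, the mismatch covers every t from 1.67 to 2.00, and the false-positive rate in favour of rose is 5% against 2.5%. The millimetre window and the probability of about 10% at a true 13 mm depend on the assumed SD of 20 mm. The conflict is also conditional on there being no separate 13 mm success rule, unless the SD is above about 25 mm.

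The word paired in the same sentence does not fit two independent arms. That is a separate defect. Correcting it alone would leave the one-tailed test in place; conversely, tests run within each arm would not assess superiority of rose at all. This is a worthwhile and inexpensive clarification, not a flaw that by itself invalidates the trial.

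**What to change.** In Section E, replace the one-tailed test with a two-sided test at 0.05 (equivalently, one-sided at 0.025) of the rose-almond difference in VAS change, and report that difference with its two-sided 95% confidence interval. In Section D, Study Sample, state the same sidedness together with the difference, SD and dropout allowance behind 30 per arm. If the 13 mm in Section A is meant as a success rule on the observed difference, say so in Section E.

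This takes a sentence or two in each place and no new data. The cost is in the stated power. If 30 per arm was a one-sided calculation, the sponsor must either restate power as about 0.70 or enrol about 38 to 39 per arm, before any dropout allowance, to keep 0.80. If it was already two-sided, nothing changes.

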Isolated acute back pain (less than 2 weeks duration) and sciatica are common complaints to the emergency department requiring acute pain management with often chronic follow-up. Their abundance in the ED as well as poorly defined treatment recommendations make them an excellent candidate to study the use of aromatherapy in the emergency department. We will replicate the Rosa damascena trials referenced above in similar protocols, patients will be recruited if they fit the attached inclusion criteria and do not meet exclusion criteria. Patients will be treated with either Almond Oil extract or Rosa damascena extract, and both the investigator and patient will be blinded to the control arm. A VAS pain scale will be recorded before treatment, after 30 minutes of treatment, and after a following 2nd 30 minutes. Patients will additionally be asked about their satisfaction and subjective changes in pain, they will be blinded to their prior VAS line placements for proper evaluation of objective pain level changes. Demographics thought to contribute to the sensation of pain, expression of pain, and response to pain treatment will additionally be collected without entangling PHI. Finally, the use of rescue medication such as NSAIDs or Narcotics at the treating physician's discretion will be recorded as an indicator of treatment failure and complication. Pain will be qualified in its type, locations, duration, immediate episodes prior to presentation, and prior remote episodes in the patient's lifetime health history. Pain will also be quantified by attempted at-home treatments prior to presentation.

Research Site

The entirety of this prospective clinical trial will be conducted at the Stony Brook Hospital Emergency Department, an ED with over 80,000 annual visits.

Study Sample

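### The chi-squared test planned for satisfaction and subjective pain ignores answer order; if the items have three or more ordered levels, a rank test is more powerful against a one-directional shift

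*Combined protocol and SAP*

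**What the plan says.** Section A (Specific Aims) makes these items secondary: "Our secondary measures include patient satisfaction", followed by rescue medication and subjective change in pain. Section D (Rationale and Overview) describes their collection in one clause: "Patients will additionally be asked about their satisfaction and subjective changes in pain". No number of levels, order or cut-point is given for either item.

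Section E names the test: "A chi-squared test will then be applied between both groups for analysis of significant differences in patient satisfaction and subjective reports". The sentence goes on to cover pain reports both before and after treatment. It names no trend, rank or exact version, and no effect measure.

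The size comes from Section D (Study Sample): "A sample size was calculated to be 30 patients for each treatment arm". The same sentence sets power at 0.80 and the significance level at 0.05. No effect size or power is given for satisfaction or subjective pain. For the VAS, Section E plans directional tests: "One-tailed paired t-Tests will be then conducted on the means".

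**The concern.** The trial asks a directional question: does rose oil relieve pain and satisfy patients more than almond oil? Pearson's chi-squared test on k levels asks only whether the two distributions differ in any way, and spreads its sensitivity over k − 1 degrees of freedom. If the answers are ordered (for example worse, same, better), a consistent shift towards better answers is easier to detect with a test that uses the order. The chi-squared result also shows neither the direction nor the size of a difference.

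The planned test covers two of the three secondary measures in Section A. At stake is whether a real shift in perceived relief or satisfaction is missed in a trial of 60 patients.

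**Working it through.** **Inputs from the documents.** 30 per arm, allocated 1:1; p below 0.05; Pearson chi-squared between arms.

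**Assumed, because the documents are silent.** Number of levels (2 to 5), the control-arm distribution, and the shift (a common odds ratio). Two-sided 0.05 is used because no sidedness is stated for these items. No dropout.

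**The plan's own figure.** The 30 per arm cannot be reproduced, because no SD is given and no power is stated for these items. For a between-arm VAS difference of 13 mm at power 0.80, SD = 13 / [(z_α + 0.842) × √(2/30)]. One-sided this gives 13 / (2.487 × 0.2582) = 20.25 mm; two-sided, 13 / (2.802 × 0.2582) = 17.97 mm. Neither figure bears on satisfaction or subjective pain.

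**Statistics compared.**
- Chi-squared with equal arms: X² = Σ (A_j − B_j)² / (A_j + B_j), on k − 1 df, where A_j and B_j are the counts at level j.
- Rank-sum: W with mid-ranks, variance (n²/12) × [(N + 1) − Σ(T_j³ − T_j) / (N(N − 1))], where n = 30, N = 60 and T_j = A_j + B_j. Normal approximation.
- With two levels z² = X² × (N − 1)/N = X² × 59/60, so the tests are practically the same.

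**One case by hand: five equal levels, odds ratio 3.** Control cumulative odds 0.25, 0.667, 1.5 and 4 are divided by 3, giving cumulative probabilities 0.077, 0.182, 0.333 and 0.571. The shifted arm is therefore 0.077, 0.105, 0.152, 0.238, 0.429, against 0.2 at each level. The noncentrality is 30 × Σ(p − q)²/(p + q) = 30 × (0.0547 + 0.0297 + 0.0067 + 0.0033 + 0.0831) = 30 × 0.1775 = 5.32. On 4 df (critical value 9.49) the power is about 0.42. If nearly all of it falls on 1 df (critical value 3.84), as for a rank test under such a shift, the power is about 0.64. Simulation gives 0.416 and 0.648.

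**Simulation: 40,000 trials per setting, power as chi-squared / rank-sum.** The odds ratio 1 column is type I error.

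| Levels (control distribution) | OR 1 | OR 1.5 | OR 2.5 | OR 3 |
|---|---|---|---|---|
| 2 (equal) | 0.052 / 0.052 | 0.125 / 0.125 | 0.397 / 0.397 | 0.517 / 0.517 |
| 3 (equal) | 0.052 / 0.050 | 0.107 / 0.134 | 0.369 / 0.470 | 0.497 / 0.606 |
| 3 (skewed) | 0.050 / 0.050 | 0.097 / 0.124 | 0.318 / 0.415 | 0.424 / 0.537 |
| 4 (equal) | 0.049 / 0.050 | 0.098 / 0.140 | 0.333 / 0.490 | 0.460 / 0.633 |
| 4 (skewed) | 0.046 / 0.049 | 0.089 / 0.132 | 0.294 / 0.452 | 0.405 / 0.589 |
| 5 (equal) | 0.049 / 0.050 | 0.088 / 0.138 | 0.296 / 0.501 | 0.416 / 0.648 |
| 5 (bell-shaped) | 0.046 / 0.050 | 0.078 / 0.138 | 0.271 / 0.487 | 0.394 / 0.636 |
| 5 (skewed) | 0.041 / 0.050 | 0.073 / 0.135 | 0.257 / 0.470 | 0.361 / 0.607 |

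Smaller runs at odds ratio 3.5 agree: 0.61 / 0.71 with three levels, 0.58 / 0.75 with four, and 0.50–0.54 / 0.73–0.76 with five.

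**Where the rank test does worse.** Take three levels, 0.2, 0.6, 0.2 in one arm and 0.4, 0.2, 0.4 in the other. The noncentrality is 30 × (0.04/0.6 + 0.16/0.8 + 0.04/0.6) = 10, but the average ranks are equal. Power is 0.839 for chi-squared and 0.063 for the rank test. Across five assumed non-monotone patterns the rank test loses 45 to 78 points.

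**Small counts.** The expected count per arm is T_j × 30/60, which is below 5 whenever fewer than 10 of the 60 choose that level. With five levels this happened in 81 to 99% of simulated tables. Yet the type I error of chi-squared stayed between 0.041 and 0.052.

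**The case against.** The strongest reply is that the premise is not in the documents. Nothing says that the answers are ordered or have more than two levels, and the format may be fixed on the patient data sheet that Section D (Procedures) mentions. For yes/no items chi-squared is suitable. This stands: a reader might infer that the planned test certainly loses 10 to 25 points, but the documents support only a conditional loss.

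A reader might also infer that a rank test costs nothing. It costs no patients and no type I error, but it is nearly blind to polarised answers. That pattern is conceivable here: Section G lists dislike of the assigned scent as a risk, and Section D (Procedures) expects patients to recognise their scent. The point stands as a drawback. It does not reverse the recommendation, because the trial asks whether one oil does better and not whether opinions are more divided.

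Two other strong readings fail. Sparse tables do not make the chi-squared test invalid here, since no inflation of type I error was seen. Nor is it established that the plan tests baseline reports between arms: the words on pre- and post-treatment pain may simply mean change, as in Sections A and D. The phrase needs clarifying, no more.

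Finally, a rank-sum p-value gives no effect size either. That is correct, so an estimate must be added separately.

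**Conclusion.** The point holds as a conditional, minor improvement. With two levels nothing is lost. With three to five ordered levels, 30 per arm and a one-directional shift, chi-squared gives up about 2 to 6 points at odds ratio 1.5. At odds ratios 2.5 to 3.5 it gives up about 9 to 11 points (three levels), 16 to 19 (four) or 20 to 25 (five).

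These figures rest on assumed scales, assumed proportional-odds shifts, two-sided testing and complete data. The documents supply only the sample size, the significance level and the name of the test. The measures are secondary and unpowered, so the VAS comparison is unaffected.

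**What to change.** State the response levels of both items in the protocol, and replace the chi-squared sentence in Section E with:

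> Post-treatment satisfaction and subjective change in pain will be compared between arms by the tie-corrected Wilcoxon rank-sum test (equivalent to chi-squared for a two-level item), and the distribution of answers will be shown by arm.

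Add a between-arm effect estimate with a 95% confidence interval. This could be a common odds ratio, or the probability that a patient in one arm answers better than a patient in the other. If pre-treatment reports are collected separately, describe them by arm and do not test them.

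Use the tie-corrected normal approximation and not a permutation p-value. In a simulation of 2,000 trials per setting, the permutation version cost about 9 to 11 points on a two-level item and 0 to 3 points with three to five levels.

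The cost is a few lines of analysis text, with no new data and no more patients. A common odds ratio adds a proportional-odds assumption that can be checked only weakly with 30 per arm; the probability measure avoids it. The rank test's weakness against polarised answers remains, which is why the full distribution should be shown.
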